6.21. Pharmacokinetic (PK) Samples

Plasma and urine PK samples will be collected as described below for assessment of GS-6615 concentrations and metabolites for PK characterization and future population PK studies of GS-6615 in the HCM population.

Detailed instructions for the processing, packaging, and shipping of PK samples will be provided in a separate manual.

6.21.1. Plasma PK Samples

Two PK samples will be drawn at the Randomization visit. The first sample should be collected before the subject has taken the first dose of study drug. The second sample should be collected approximately 2-3 hours after the subject has taken the first dose of study drug. If 2-3 hours postdose is not possible, the PK sample should be collected as late as possible before the subject leaves the site.

Two PK samples will be drawn at all visits after Randomization through the end of the double-blind treatment period and during the open-label extension period at the OLE Week 12 and OLE Week 24 visits. The first sample should be obtained before the subject has taken the daily study drug dose on site. The subject will then take the study drug while at the site and the second PK sample should be collected approximately 3 hours postdose. If 3 hours postdose is not possible, the second PK sample should be collected as late as possible before the subject leaves the site. For subjects who have discontinued study treatment but who are continuing in the study, a single PK sample will be collected at each follow-up visit.

A single PK sample will be collected at the Early Termination visit. The date and approximate time of the last dose of study drug should be recorded, if applicable.

A single PK sample will be collected starting at each open-label extension visit starting at OLE Week 48 and at the 30-day Follow-up visit. The date and approximate time of the last dose of study drug should be recorded, if applicable.

6.21.2. Urine PK Samples

A single urine PK sample will be collected predose at all visits starting at Week 2 visit through the end of the double-blind treatment period and during the open-label extension period at the OLE Week 12 and OLE Week 24 visits. For subjects who have discontinued study treatment but who are continuing in the study, urine PK samples will continue to be collected at each follow-up visit.

A single urine PK sample will be collected at the Early Termination visit. The date and approximate time of the last dose of study drug should be recorded, if applicable.

6.22. NT-proBNP and High-sensitivity Troponin T (hsTnT) Samples

Blood samples for analysis of NT-proBNP and hsTnT prognostic biomarkers will be collected at Screening, Week 12, and Week 24 visits. Refer to Section 3.7.1 for further detail on biomarker sample collection.

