3.7. Biomarker Testing

3.7.1. Biomarker Samples to Address the Study Objectives

Blood samples will be collected and used to evaluate the association of systemic biomarkers with study drug response, including efficacy and/or adverse events and to increase knowledge and understanding of the biology of HCM and related diseases. The specific analyses will include NT-proBNP and high-sensitivity Troponin T (hsTnT), but will not be limited to the biomarkers listed. Because biomarker science is a rapidly evolving area of investigation, and adverse events in particular are difficult to predict, it is not possible to specify prospectively all tests that will be done on the specimens provided. The testing outlined is based upon the current state of scientific knowledge and may change during or after the end of the study to remove tests no longer indicated and/or to add new tests based upon the growing state of art knowledge.

Blood samples will be collected from all subjects at Screening, Week 12, and Week 24 visits for analysis of NT-proBNP and high-sensitivity Troponin T (hsTnT). These are validated biomarkers of myocardial wall stress and microvascular ischemia respectively that have been shown to predict long-term prognosis in patients with HCM {Coats et al 2013}, {Kubo et al 2013}.

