6.8.1. Early Termination Visit

If during the double-blind treatment period, in addition to study drug discontinuation, a subject prematurely discontinues study participation, the subject will be asked to return to the study center for the Early Termination (ET) Visit. When possible, the ET Visit should be performed within 48 hours of decision to prematurely withdraw.

The following will be performed and documented at the ET visit:

- Confirm reason for permanent withdrawal and that subject is not willing to continue to perform study-related follow-up and procedures until study end of the double-blind treatment period. If appropriate, discuss options for study drug dose modification per Section 5.3.1.
- Obtain consent for vital status collection to occur every 3 months until end of double-blind treatment period as described in Section 6.8.2
- Abbreviated physical examination including vital signs, as described in Sections 6.18 and 6.19
- Standard 12-lead resting ECG as described in Section 6.12

- For subjects with ICDs, perform ICD interrogation as described in Section 6.15
- Complete Cardiopulmonary Exercise Testing (CPET) using the Modified Naughton Protocol as described in Section 6.11 and according to the study-specific CPET Manual if subject prematurely discontinued prior to Week 24 study visit
- MLHFQ administration as described in Section 6.16 if subject prematurely discontinued prior to Week 24 visit
- Perception of Treatment Assignment Questionnaire administration as described in Section 6.17 if subject prematurely discontinued prior to Week 24 visit
- ECHO as described in Section 6.14
- Blood and urine sample collection for Clinical Laboratory Assessments as described in Section 6.20
- Urine pregnancy test for females of childbearing potential only
- Plasma and urine PK sample collection at a single timepoint as described in Section 6.21
- Review of concomitant medications
- Review of adverse events
- Collect and review used and unused study drug for accountability and calculate compliance, if applicable

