6.11. Cardiopulmonary Exercise Testing (CPET)

Subjects will undergo an upright treadmill CPET using the Modified Naughton Protocol ([Appendix 3](#)) at Screening, Week 12, Week 24 study visits, and if applicable, Early Termination visit. If possible, all exercise tests should be performed in the morning and the same study team members should perform all subjects' tests.

At Screening, the investigator will review CPET data for Peak VO₂ result to confirm subject eligibility.

A core exercise physiology laboratory will collect cardiopulmonary data and provide centralized blinded adjudication of the primary endpoint (Peak VO₂) and related secondary endpoints.

Details of the core exercise physiology laboratory procedures including site qualification, instructions for transmittal of data, and analysis of all ECG and ventilatory gas exchange data collected during the study will be specified in the CPET study manual.

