6.13. ZIO[®] XT Patch

The ZIO[®] XT Patch will be worn for 14 day periods throughout the study as outlined in Section 6 and in Appendix 2.

The ZIO[®] XT Patch is a single use continuously recording ECG monitor. Used ZIO[®] XT Patches will be returned to iRhythm for analysis. Instructions for ZIO[®] XT Patch use and return for processing will be provided in a study-specific ZIO[®] XT Patch manual.

Investigators should reference the study manual for warnings and precautions for ZIO[®] XT Patch use prior to applying the ZIO[®] XT Patch to the subject.

The site staff will apply the ZIO[®] XT Patch on site following the instructions provided in the study manual, review instructions for wear with the subject, and instruct the subject on timing and removal of the patch. At the conclusion of the 14 day wear period, the subject will remove the ZIO[®] XT Patch at home and will return it to the site at the next scheduled study visit. Based on individual wear experiences actual wear time may be less than 14 days in some subjects (eg, due to intolerable skin irritation). If a subject is unable to wear the patch for the full 14 day period due to poor wear practices (eg, taking long showers or doing activities that cause excessive sweating), the subject should be re-trained on proper wear practices when the next patch is applied.

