3.1.5. Biomarker Analysis Set

The primary analysis set for the biomarker (NT-proBNP, hsTnT) analyses is defined as all randomized subjects who received at least one dose of study drug and who have an NT-proBNP or hsTnT measurement both prior to study drug administration and after study drug administration. For the biomarker analysis set, subjects will be grouped based on the treatment received.

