3.8.2. Analysis Windows

Subject visits might not occur on protocol-specified days. Therefore, for the purpose of analysis, observations will be assigned to visits based on the windows presented in Table 3-1. Day 1 is the day of first dose of study drug.

Table 3-1. Visit Windows for Peak VO₂, MLHFQ, Treadmill Exercise Time, Biomarker Data, CPET 12-Lead ECG, and ICD Interrogation

Visit	Target Day	Visit Window in Day(s)
Baseline		≤ 1
Week 12	84	2–126
Week 24	168	> 126

Table 3-2. Visit Windows for ECHO

Visit	Target Day	Visit Window in Day(s)
Baseline		≤ 1
Week 2	14	2-49
Week 12	84	50–126
Week 24	168	> 126

Table 3-3. Visit Windows for Arrhythmia Burden

Visit	Target Day	Visit Window in Day(s)
Baseline		< 1
Days 1–14	1	1–21
Weeks 6–8	42	22–84
Weeks 18–20	126	> 84

The target and window are based on the start date of the 14-day ZIO[®] XT Patch period.

Table 3-4. Visit Windows for 12-Lead ECG, Vital Signs, and Clinical Laboratory Data

Visit	Target Day	Visit Window in Day(s)
Baseline		≤ 1
Week 2	14	2–28
Week 6	42	29–63
Week 12	84	64–105
Week 18	126	106–147
Week 24	168	148–210
Week 36	252	211–294
Week 48	336	295–378
Week 60	420	379–462
Week 72	504	463–546
Week 84	588	> 546 – last dose date + 30 days

All visits, including Unscheduled, Early Termination, and Follow-up visits, will be eligible for inclusion in table summaries based on the windows presented in Table 3-1, Table 3-2, and Table 3-3.

In the efficacy summary tables, Peak VO₂, treadmill exercise time, MLHFQ, ECHO, QTc interval at rest and at Peak from the exercise ECG, and biomarker results will be summarized based on values obtained at the visit using the windows in Table 3-1 or Table 3-2.

For the safety summaries, all visits other than the Follow-up visit, including Unscheduled and Early Termination visits, will be eligible for inclusion in table summaries based on the windows presented in Table 3-4.

In the safety summary tables for 12-lead ECG and vital signs, data obtained after the last dose date plus 30 days will be excluded from the summaries, but will be included in the listings.

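### The Early Termination visit draws blood but schedules no NT-proBNP/hsTnT sample and does not ask for an outstanding ZIO XT Patch

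*Protocol*

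**What the plan says.** **Biomarkers.** Protocol 6.22: "Blood samples for analysis of NT-proBNP and hsTnT prognostic biomarkers will be collected at Screening, Week 12, and Week 24 visits". Section 3.7.1 names the same three visits. By contrast, 6.11 places CPET "at Screening, Week 12, Week 24 study visits, and if applicable, Early Termination visit".

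**ET visit.** The list in 6.8.1 includes "Complete Cardiopulmonary Exercise Testing (CPET) using the Modified Naughton Protocol as described in Section 6.11" for subjects leaving before Week 24. It also includes MLHFQ on the same condition, ECHO, ICD interrogation, a single-timepoint PK sample, and "Blood and urine sample collection for Clinical Laboratory Assessments as described in Section" 6.20. NT-proBNP/hsTnT and patch collection are not on the list.

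**Patch.** Sections 6.3, 6.4.3 and 6.4.7 tie the patches started at Randomization, Week 6 and Week 18 to collection at Weeks 2, 12 and 24. Section 6.13 adds only that the subject removes the patch at home and "will return it to the site at the next scheduled study visit".

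**Analysis.** SAP 3.1.5 admits a subject to the biomarker set only with a "measurement both prior to study drug administration and after study drug administration". SAP 3.8.2 states: "All visits, including Unscheduled, Early Termination, and Follow-up visits, will be eligible for inclusion in table summaries". That rule covers the windows for biomarkers (Table 3-1) and arrhythmia burden (Table 3-3). SAP 3.6 imputes neither.

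**The concern.** An early leaver is asked for a treadmill test, a questionnaire and an echocardiogram, and gives blood, but the tube for the wall-stress and ischemia markers is not on the list. No reason is given for treating these markers differently. The same subject may hold a rhythm recording, possibly complete, that no ET item asks for.

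At stake is the completeness of two sets of results. Subjects who withdraw before Week 12 drop out of the biomarker set, while their CPET, MLHFQ and ECHO from the ET visit can be used. For rhythm data, the recording at risk covers the period shortly before withdrawal, and the protocol synopsis names arrhythmia burden among the safety criteria.

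**Working it through.** The plan states no figure on this point, so the check is a comparison of the schedule sections, followed by simple day counts.

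**1. Schedule side by side**

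| Assessment | Own section names ET? | In the 6.8.1 list? | ET column, Appendix 2 |
|---|---|---|---|
| CPET | yes (6.11) | yes, if before Week 24 | marked |
| MLHFQ | yes (6.16) | yes, if before Week 24 | marked |
| ICD interrogation | yes (6.15) | yes | marked |
| ECHO | by reference to Section 6 and Appendix 2 (6.14) | yes | marked |
| Laboratory blood | by reference to Section 6 and Appendix 2 (6.20) | yes | marked |
| Plasma PK | yes (6.21.1) | yes | marked |
| NT-proBNP/hsTnT | no (3.7.1, 6.22) | no | blank |
| Collect ZIO XT Patch | no (6.13) | no | blank |

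SAP Appendix 1 repeats the two blanks.

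**2. Biomarker consequence by time of study withdrawal**

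- The Week 12 visit is Day 84 ± 7 (6.4.5), so the first scheduled post-dose draw is no earlier than Day 84 − 7 = Day 77.
- Withdrawal before the Week 12 visit: no scheduled post-dose value, so the subject is outside the biomarker set.
- Withdrawal between Weeks 12 and 24: the Week 12 value is kept and there is no later one.

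**3. Patch consequence, by nominal visit days**

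- Day 1 patch, collected Day 14: 14 days.
- Week 6 patch, collected Week 12: 84 − 42 = 42 days.
- Week 18 patch, collected Week 24: 168 − 126 = 42 days.
- Total: 14 + 42 + 42 = 98 days; 98/168 = 58%.
- Wear time within this is 3 × 14 = 42 days. On the other 98 − 42 = 56 days the 14-day recording is finished and awaits return.

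**4. Number of subjects**

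The documents give no dropout rate. If 5%, 10% or 20% of the 180 planned subjects withdrew before Week 24 (an assumption), that would be 9, 18 or 36 subjects. How these would split around Week 12 is unknown.

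**5. Where an ET record would land in the SAP**

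- Biomarkers: Table 3-1 sends any record on Days 2–126 to Week 12 and any later one to Week 24. A Day 10 ET sample, 84 − 10 = 74 days before target, would be reported as Week 12 if it were the only record. If a Week 12 draw also exists, SAP 3.8.3 selects the record closest to Day 84.
- Patch: Table 3-3 assigns by start date, so a patch recovered at ET falls into its intended period without a new rule.

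**The case against.** The strongest reply is that little is lost and that the documents do not contradict each other. Most of it stands.

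- A reader might infer from SAP 3.8.2 that the analysis expects an ET biomarker sample. It does not. The sentence is a general eligibility rule that also covers the Follow-up visit, where no CPET, MLHFQ, ECHO or biomarker is scheduled.
- A reader might infer that the biomarker and rhythm results describe only subjects who stayed. That goes too far. Protocol 5.3.1 and 6.8 seek to keep subjects who stop drug in the study with its procedures. Leavers after Week 12 keep their Week 12 biomarkers, and patches already returned still count.
- A reader might infer from the sponsor's termination that ET visits before Week 24 were common. SAP 2 says only that the study stopped before the end of the double-blind phase. That phase could run to about 20 months, and the SAP's windows extend to Week 84. A sponsor stop is also no evidence of exits caused by worsening disease.
- Nothing forbids handing in a patch at ET, and 6.13 can be read loosely to allow it. This is correct, but permission is not a request, and the ET list is what a site works from.
- SAP 4.1 summarises reasons for exclusion from analysis sets. That discloses the biomarker loss but recovers nothing.

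What remains is the omission itself and its direct consequence for subjects who withdraw from the study.

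**Conclusion.** The omission is confirmed in 3.7.1, 6.8.1, 6.13, 6.22 and Appendix 2. It matters for subjects who withdraw from the study before Week 24, not for those who only stop drug.

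Severity is minor. SAP 6.6 provides no inferential statistics for exploratory endpoints, and SAP 1 limits the synoptic report to the relevant ones. Their definitions are redacted, so the effect on any retained summary cannot be judged. The patch part also touches arrhythmia burden as a safety criterion in the synopsis. No primary, secondary or formally tested result changes.

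Two limits apply to the size. The 58% is calendar time at nominal visit days. Reading it as the share of leavers whose recording is lost would require evenly spread exits and no site accepting a patch at ET, and the documents support neither. Loss that differs by arm is possible, but nothing in the documents shows it.

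**What to change.** For subjects leaving before Week 24, add to Protocol 3.7.1, 6.8.1, 6.13, 6.22 and the ET column of Appendix 2 (with its copy in SAP Appendix 1):

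1. NT-proBNP and hsTnT tubes from the blood draw already made at ET. Keep the order relative to CPET that 6.4.5 and 6.4.9 recommend for Weeks 12 and 24, where other blood sampling follows CPET. Drawing before exercise at ET would put pre-exercise values beside post-exercise ones.
2. Collection of any outstanding ZIO XT Patch, assigned by start date under SAP Table 3-3.

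In the SAP, flag ET biomarker values as ET records, so that a sample from early in the Days 2–126 window is not presented as an ordinary Week 12 value.

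The cost is one tube and assay per early leaver at an existing venipuncture, the hand-in of a patch, and a small SAP flag. No visit is added.

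The schedule change cannot help the study already terminated. For its report, give by arm the number of early leavers without a post-dose biomarker and the number with an unreturned patch.

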7. ADVERSE EVENTS

7.1. Definitions of Adverse Events, Adverse Reactions, and Serious Adverse Events

7.1.1. Adverse Events

An adverse event (AE) is any untoward medical occurrence in a clinical study subject administered a medicinal product, which does not necessarily have a causal relationship with the treatment. An AE can therefore be any unfavorable and/or unintended sign, symptom, or disease temporally associated with the use of a medicinal product, whether or not considered related to the medicinal product. AEs may also include pre- or post- treatment complications that occur as a result of protocol specified procedures, lack of efficacy, overdose, drug abuse/misuse reports, or occupational exposure. Pre-existing events that increase in severity or change in nature during or as a consequence of participation in the clinical study will also be considered AEs.

An AE does not include the following:

- Medical or surgical procedures such as surgery, endoscopy, tooth extraction, and transfusion. The condition that led to the procedure may be an adverse event and must be reported.
- Pre-existing diseases, conditions, or laboratory abnormalities present or detected before the screening visit that do not worsen
- Situations where an untoward medical occurrence has not occurred (eg, hospitalization for elective surgery, social and/or convenience admissions)
- Overdose without clinical sequelae (see Section 7.5.1)
- Any medical condition or clinically significant laboratory abnormality with an onset date before the consent form is signed and not related to a protocol-associated procedure is not an AE. It is considered to be pre-existing and should be documented on the medical history eCRF.

7.1.2. Serious Adverse Events

A serious adverse event (SAE) is defined as an event that, at any dose, results in the following:

- Death
- Life-threatening (Note: The term “life-threatening” in the definition of “serious” refers to an event in which the subject was at risk of death at the time of the event; it does not refer to an event that hypothetically might have caused death if it were more severe.)
- In-patient hospitalization or prolongation of existing hospitalization

- Persistent or significant disability/incapacity
- A congenital anomaly/birth defect
- A medically important event or reaction: such events may not be immediately life-threatening or result in death or hospitalization but may jeopardize the subject or may require intervention to prevent one of the other outcomes constituting SAEs. Medical and scientific judgment must be exercised to determine whether such an event is a reportable under expedited reporting rules. Examples of medically important events include intensive treatment in an emergency room or at home for allergic bronchospasm; blood dyscrasias or convulsions that do not result in hospitalization; and development of drug dependency or drug abuse. For the avoidance of doubt, infections resulting from contaminated medicinal product will be considered a medically important event and subject to expedited reporting requirements.

7.1.3. Clinical Laboratory Abnormalities and Other Abnormal Assessments as Adverse Events or Serious Adverse Events

Laboratory abnormalities without clinical significance are not recorded as AEs or SAEs. However, laboratory abnormalities (eg, clinical chemistry, hematology, and urinalysis) that require medical or surgical intervention or lead to study drug interruption, modification, or discontinuation must be recorded as an AE, as well as an SAE, if applicable. In addition, laboratory or other abnormal assessments (eg, electrocardiogram, x-rays, vital signs) that are associated with signs and/or symptoms must be recorded as an AE or SAE if they meet the definition of an AE or SAE as described in Sections 7.1.1 and 7.1.2. If the laboratory abnormality is part of a syndrome, record the syndrome or diagnosis (eg, anemia), not the laboratory result (ie, decreased hemoglobin).

7.2. Assessment of Adverse Events and Serious Adverse Events

The investigator or qualified subinvestigator is responsible for assessing AEs and SAEs for causality and severity, and for final review and confirmation of accuracy of event information and assessments.

7.2.1. Assessment of Causality for Study Drugs and Procedures

The investigator or qualified subinvestigator is responsible for assessing the relationship to study drug using clinical judgment and the following considerations:

- **No:** Evidence exists that the adverse event has an etiology other than the study drug. For SAEs, an alternative causality must be provided (eg, pre-existing condition, underlying disease, intercurrent illness, or concomitant medication).
- **Yes:** There is reasonable possibility that the event may have been caused by the study drug.

It should be emphasized that ineffective treatment should not be considered as causally related in the context of adverse event reporting.

The relationship to study procedures (eg, invasive procedures such as venipuncture or biopsy) should be assessed using the following considerations:

- **No:** Evidence exists that the adverse event has an etiology other than the study procedure.
- **Yes:** The adverse event occurred as a result of protocol procedures (eg, venipuncture).

